6.1.3. Primary target variable

The primary endpoint will be the change of best corrected visual acuity in ETDRS Letters score at month 12 when compared with baseline. This endpoint will be analysed by analysis of covariance (ANCOVA) with the baseline value as covariate (type II SS will be used since no interaction terms are included in the model).

The null hypothesis is:

$$H_0: \mu_{iDC} = \mu_{rDC}$$

and the alternative hypothesis is:

$$H_1: \mu_{iDC} \neq \mu_{rDC}$$

where μ_{iDC} is the mean of the differences in ETDRS Letters score between month 12 and baseline for the investigational arm (intensified diabetic control) and μ_{rDC} is the mean of the differences in ETDRS Letters score between month 12 and baseline for the control arm (regular diabetic control).

ITT population is used for the primary efficacy analysis. If no ETDRS Letter score is available at month 12 the closest measurement (could be before or after 12 month) which was at least after 3 months will be used for the analysis.

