6.1.6. Sensitivity and Subgroup analyses

A sensitivity analysis for the primary endpoint based on the PP population will be performed.

Another sensitivity analysis will assess the influence of the assumption of normality for the primary analysis by transforming the data with the natural logarithm. The ANCOVA described in section 6.1.3 will be applied in the same way on the transformed data.

The primary and secondary endpoint except number of neovascular complications and rates of ocular and of systemic AEs will be analysed by descriptive statistics and statistical methods mentioned above within the following subgroups defined by the following potentially prognostic baseline variables:

- HbA1c: $\geq 9\%$
- HbA1c: $\geq 7,5\%$, $< 9\%$

- HbA1c: $\geq 6,5\%$, $< 7,5\%$
- Intravitreal treatment with ranibizumab before trial entry (yes vs no)
- Size of macula edema $>400\mu\text{m}$
- BCVA (>65 vs ≤ 65)

For the sake of subgroup analysis, the ITT population will be used.

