6.2. Sample size calculation

The calculation of the sample size is based on the primary endpoint. It is of interest to discover the difference between two treatment groups, and we assume that the average difference between treatments in the primary endpoint is 2.0 ($\delta=2.0$). Assuming the standard deviation of the change of best corrected visual acuity in ETDRS letters score over 12 months be $\sigma=3.5$. Then, the study is designed to detect a decrease of 0.571 times of standard deviation in the primary endpoint for the treatment arm with intensified diabetic control program ($\delta/\sigma\approx 0.571$). With a two-sided alpha of 5% and a power of 85%, a sample size of 112 patients is required to detect this difference. Given the allocation ratio of 1:1 between two treatment arms, 56 patients per arm are required. In order to take drop-outs into account, approx 7% increase in sample size is anticipated which leads to the randomisation of 60 patients per treatment arm ($56*1.07=60$). Thus, altogether, 120 patients will be included in the trial. Sample size calculation was performed with SAS 9.4.

7. Safety

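### Section 6.1.6 tests the arms separately within each baseline stratum and specifies no treatment-by-subgroup interaction, so it cannot show whether the effect differs between strata

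*Combined protocol and SAP*

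**What the plan says.** Section 6.1.6 covers all endpoints except neovascular complications and adverse event rates. Each is to be analysed by descriptive statistics and by the "statistical methods mentioned above within the following subgroups defined by the following potentially prognostic baseline variables". The methods referred to are:

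- ANCOVA for the primary endpoint (section 6.1.3);
- ANOVA for the number of injections, repeated-measures ANOVA for BCVA and macular thickness, and log-rank test plus Cox model for time to target HbA1c (section 6.1.4).

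The subgroups are three HbA1c bands, prior ranibizumab (two levels), BCVA above 65 versus 65 or below, and macular oedema above 400 µm. No complementary oedema stratum is listed.

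The ANCOVA has none of the terms that would compare effects between strata: "type II SS will be used since no interaction terms are included in the model". Section 6.1.4 names one interaction, treatment by time, and includes no covariates in the ANOVA or the Cox model. Section 6.1.6 gives no rule for reading the subgroup results. Section 4.2 states that randomisation is not stratified. Section 6.1 labels the trial therapeutic-exploratory and leaves further detail to a statistical analysis plan; no separate text of that kind is in the documents.

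**The concern.** Splitting the trial by a baseline variable and comparing the arms in each part invites one question: does the effect of intensified diabetes control depend on that variable? Two separate p-values do not answer it. One stratum can reach significance and the other miss it because each is small, even though the true effects are equal. The quantity that answers the question is the difference between the stratum effects with its standard error, and the plan never estimates it.

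At stake is how the subgroup tables will be read. A table with a significant result in one HbA1c band or in previously untreated eyes, and none elsewhere, looks like evidence about who benefits. With strata of this size such a table can easily arise by chance.

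**Working it through.** **Inputs (section 6.2).** On the effect, the section says "we assume that the average difference between treatments in the primary endpoint is 2.0"; the SD is 3.5 letters. On size: "With a two-sided alpha of 5% and a power of 85%, a sample size of 112 patients is required to detect this difference", that is 56 per arm, raised to 60 per arm for drop-out. Stratum sizes are not given, so every split below is an assumption, as is equal allocation within strata.

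**Formula.** With m patients per arm, power is that of a two-sided two-sample t-test at 5%, from the noncentral t distribution with 2m − 2 degrees of freedom and noncentrality δ / (σ√(2/m)).

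**The plan's own figure.** m = 56: noncentrality 2 / (3.5 × √(2/56)) = 3.02, power 85.0%. The stated 112 is reproduced. 56 × 1.07 = 59.9, hence 60 per arm.

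**Two-level factor, even split, true effect 2.0 letters in both halves.**

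- N = 112: m = 28 per arm per half, noncentrality 2.14, power 55.6%. Exactly one half significant: 2 × 0.556 × 0.444 = 49.4%.
- N = 120: m = 30, noncentrality 2.21, power 58.6%. Exactly one: 2 × 0.586 × 0.414 = 48.5%.

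Among trials of this kind with a significant overall result, the split verdict occurs 52-53% of the time (simulation, normal approximation).

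**Uneven splits.** With stratum powers p1 and p2, the rate is p1(1 − p2) + p2(1 − p1).

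| Split | N = 112 | N = 120 |
|---|---|---|
| 60:40 | 51.0% | 50.3% |
| 70:30 | 55.7% | 55.4% |
| 80:20 | 63.0% | 63.5% |
| 90:10 | 72.5% | 73.9% |

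**Three equal HbA1c strata.** A third of 56 is 18.7 per arm (power 39.7%); a third of 60 is 20 per arm (power 42.1%). The chance of a mixed verdict is 1 − p³ − (1 − p)³ = 71.8% and 73.1% respectively.

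**Sensitivity, even two-level split.**

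| True effect in both halves | SD | N = 112 | N = 120 |
|---|---|---|---|
| 0 | 3.5 | 9.5% | 9.5% |
| 1 letter | 3.5 | 29.9% | 31.1% |
| 1.5 letters | 3.5 | 45.5% | 46.7% |
| 2.5 letters | 3.5 | 37.8% | 34.7% |
| 3 letters | 3.5 | 20.7% | 17.4% |
| 2 letters | 3.0 | 42.9% | 40.4% |
| 2 letters | 5.0 | 43.0% | 44.3% |
| 2 letters | 7.0 | 29.9% | 31.1% |

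**The interaction instead.** For an even split the difference between stratum effects has SE 3.5 × √(4/m): 1.32 letters at m = 28 and 1.28 at m = 30.

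- False signal when the effects are equal: 5% by construction (5.0% in simulation).
- 95% CI half-width, 1.96 × SE: 2.6 and 2.5 letters.
- Power for a true 2-letter difference in effects (normal approximation): 33% and 35%.
- Difference detectable with 80% power, 2.80 × SE: 3.7 and 3.6 letters.

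**The case against.** **The subgroup work is exploratory, and no objective concerns effect modification.** This is fair, and it limits the consequence. Section 2 poses no such question, section 6.1.6 calls the variables prognostic, and no decision depends on the subgroups. A reader might infer that the protocol intends to claim effect modification; the documents do not say so. But the tables will be read for differences between strata, and the label does not turn separate tests into a comparison.

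**Further detail is left to the analysis plan.** An interaction could be added there, so the documents do not support saying that none will ever be tested, only that none is specified in them. Section 6.1.6 nevertheless already fixes the method as testing within strata.

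**The rate of about one half is conditional.** This stands. A reader might infer that a split verdict arises half the time whenever the effect is the same everywhere. The sensitivity table shows otherwise. The figure needs a common effect near 2 letters, a residual SD near 3.5 and an even two-level split. Baseline adjustment in the ANCOVA may bring the residual SD below 3.5, which lowers the rate. Only BCVA and prior ranibizumab are listed with two levels.

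**Interaction tests are underpowered here.** True. The CI half-width exceeds the whole planned effect. The gain is fewer false contrasts and visible uncertainty, not a firm answer on who benefits.

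**The number of tests.** A reader might add a multiplicity charge. That is a separate matter: interaction testing reduces the number of comparisons but does not control the error rate across them.

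**Conclusion.** The point holds in conditional form. As written, section 6.1.6 tests within strata and no treatment-by-subgroup contrast is specified in the documents, so the planned analysis cannot show whether the effect differs.

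Under the plan's own effect, SD and sample size, an evenly split two-level factor gives a spurious split verdict 48.5-49.4% of the time, against 5% for one interaction test. More uneven splits raise the rate, to 55-74% between 70:30 and 90:10, and three equal HbA1c strata give a mixed verdict about 72-73% of the time. The rate falls for common effects well away from 2 letters, to 9.5% with no effect. All these figures rest on assumed stratum sizes.

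The oedema factor has a further gap: with only the stratum above 400 µm listed, there is nothing to compare it with. The primary analysis, the sample size and the stated objectives are not affected.

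**What to change.** For each subgroup variable, revise section 6.1.6 or the analysis plan as follows:

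- Add the subgroup variable and a treatment-by-subgroup term to the endpoint's model: ANCOVA for the primary endpoint, ANOVA for injection counts, repeated measures for BCVA and thickness (naming the time point of the contrast). For time to target HbA1c, use the Cox model in place of within-stratum log-rank tests, since a log-rank test has no interaction term.
- List the stratum of 400 µm or below, so that oedema size has a comparison.
- Report the interaction estimate with its 95% CI. Give stratum effects as estimates with CIs, without within-stratum significance claims, and label all of it exploratory.
- State the low power: about 33-35% for a 2-letter difference in effects and a CI half-width of about 2.5-2.6 letters under an even split.

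The cost is wording and some extra model terms. No additional patients or measurements are needed. The models do change: sections 6.1.3 and 6.1.4 currently leave such terms out of the ANCOVA, ANOVA and Cox models, so the text should say that the added terms apply to the subgroup analyses only and that the primary ANCOVA stays as it is.

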6.1.7. Interim analysis

No interim analysis is planned.

6.1.8. Handling of missing data

If not stated otherwise no imputations of missing values will be performed.

6.2. Sample size calculation

The calculation of the sample size is based on the primary endpoint. It is of interest to discover the difference between two treatment groups, and we assume that the average difference between treatments in the primary endpoint is 2.0 ($\delta=2.0$). Assuming the standard deviation of the change of best corrected visual acuity in ETDRS letters score over 12 months be $\sigma=3.5$. Then, the study is designed to detect a decrease of 0.571 times of standard deviation in the primary endpoint for the treatment arm with intensified diabetic control program ($\delta/\sigma\approx 0.571$). With a two-sided alpha of 5% and a power of 85%, a sample size of 112 patients is required to detect this difference. Given the allocation ratio of 1:1 between two treatment arms, 56 patients per arm are required. In order to take drop-outs into account, approx 7% increase in sample size is anticipated which leads to the randomisation of 60 patients per treatment arm ($56*1.07=60$). Thus, altogether, 120 patients will be included in the trial. Sample size calculation was performed with SAS 9.4.

7. Safety

7.1. Definitions of adverse events and adverse drug reactions

7.1.1. Adverse event

An adverse event (AE) is any untoward medical occurrence in a trial subject administered an IMP. There does not necessarily have to be a causal relationship with this treatment.

All events occurring after the first administration of the IMP until 30 days after the patient has stopped the treatment must be documented by the investigator or designee.

The deterioration of a preexisting illness is also an AE in the context of a clinical trial, i.e. medical conditions/diseases present before study treatment are only considered adverse events if they worsen after start of study treatment. Abnormal laboratory values or test results constitute adverse

events only if they induce clinical signs or symptoms, require study treatment discontinuation or require therapy.

Pregnancy

For reasons of drug safety, the occurrence of a pregnancy during the conduct of this trial is to be regarded as an AE.

The investigator or a member of the local trial team will inform the sponsor or designee without delay about any pregnancy that occurs during the trial at latest within 24 hours of being made aware of it. This will be documented on a separate report form ("Clinical trial pregnancy form"). If additional informations are known these must also be sent by the investigator within 24 hours of awareness. The pregnant women will be asked to give separate informed consent for pregnancy follow up. For tracing health of the newborn baby after delivery both parents have to give an informed consent.

In case of pregnancy study medication has to be stopped immediately.

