Study endpoints:	Primary endpoint: 
• Change of best corrected visual acuity in ETDRS letters score at month 12 when compared with baseline (measured by the difference in ETDRS letters score between month 12 and baseline) Secondary endpoints: 
• Number of treatments with ranibizumab up to 6, 12, 18 and 24 months of treatment respectively• Mean average change in BCVA at 6, 12, 18 and 24 months after initial treatment• Macular thickness (as measured with OCT) at 6, 12, 18 and 24 months after initial treatment• Time to reach target HbA1c• Number of neovascular complications: need for panretinal laser photocoagulation (PRP)• Rates of ocular and of systemic AEs (retinal detachment, central retinal artery occlusion, endophthalmitis; rates of stroke, myocardial infarction, severe hypoglycemia)

Medical condition:	Diabetic patients with visual impairment due to diabetic macular edema (DME)								
Principal inclusion criteria:	
 • Patients with diabetic macular edema relevant to visual acuity • OCT central retinal thickness $\geq 250\mu\text{m}$ • HbA1c $> 6,5\%$ at initial visit • BCVA ≤ 0.8 and ≥ 0.05 • Age ≥ 18 years • Written patient informed consent given 								
Principal exclusion criteria:	
 • Previous treatment with intravitreal drugs in last 6 months • Vitreous hemorrhage as a consequence of proliferative retinopathy • Pregnancy • Blood pressure of $\geq 180/100$ (or uncontrolled pressures under pharmacological therapy) • Chronic systemic or ocular inflammatory/autoimmune diseases (e.g. inflammatory bowel disease, Addison's disease, Cushing Syndrome, Uveitis) • Systemic cortisone or anti-VEGF therapy • Acute systemic or ocular infectious diseases 								
Name of investigational medicinal product (IMP):	Ranibizumab (Lucentis®)								
Investigational medicinal product – dosage and method of administration:	Ranibizumab – three initial monthly intravitreal injections (0.05 mg) and subsequent injections until visual acuity reached maximum (maximum of visual acuity defined as stable visual acuity under treatment with ranibizumab on three consecutive monthly control visits)								
IMP or therapy used as a comparator – dosage and method of administration:	not applicable								
Duration of treatment:	12 months treatment period with Ranibizumab Total follow-up is 12 months (with PRN treatment option)								

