4.6.1. Treatments to be given

In all patients (in both study arms) the diabetic macular edema will be treated with intravitreally given ranibizumab.

Dosage and administration of Ranibizumab

Injections are administered according to the current summary of product characteristics Lucentis®, i.e. monthly until maximum BCVA can be observed:

Starting at visit 1, ranibizumab will be administered intravitreally in a multiple-dose regimen of 0.5 mg of ranibizumab every month for a total of 3 injections and as a PRN treatment thereafter (subsequent injections until maximum BCVA is observed).

Injection is discontinued when

- no BCVA improvement in spite of treatment is seen after the first three injections (i.e. after three consecutive monthly visits)

BCVA assessments will take place monthly. Monthly injections are resumed when

- decrease in BCVA due to worsening of DME in the opinion of the investigator is observed

Injections are continued until BCVA improvement is seen after three consecutive monthly visits.

If a subject is unable to receive study drug because of medical or personal reasons, treatment should be resumed within 2 weeks of the scheduled treatment. If a subject is unable to receive study drug within 2 weeks of the scheduled treatment, the subject will be allowed to miss the scheduled dose and resume treatment at the next regularly scheduled time. Dosing should not occur more frequently than every 4 weeks. Missed doses will not be replaced.

Ranibizumab Injection

Procedures will be implemented to minimise the risk of potential adverse events associated with serial intraocular injections (e.g., endophthalmitis). Aseptic technique must be observed by clinic staff involved in the injection tray assembly, anesthetic preparation and administration, and study drug preparation and administration. In addition to the procedures outlined in the protocol, added safety measures in adherence to specific institutional policies associated with intraocular injections should be observed.

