4.7.4.1. Description of visits

Screening assessments should be performed 1 to 7 days before treatment start (Visit 1).

Table 2: Investigations during the clinical trial (until month 12)

Visits	Screenig	1	2	3	4	5	6	7	8	9	10	11	12
Month	-1 to -7 days	1	2	3	4	5	6	7	8	9	10	11	12
Procedure	a time frame of ± 1 week is allowed until visit 12												
Inclusion/exclusion criteria	x												
Demographic data & med. history	x												
Informed consent ¹	x												
Pregnancy status ²	x												
Randomization	x												
Study treatment		x	x	x	x ⁵	x ⁵	x ⁵	x ⁵	x ⁵	x ⁵	x ⁵	x ⁵	x ⁵
Clinical lab tests ³	x			x			x			x			x
Blood glucose and blood pressure measurement (group 1) (regular diabetic control) ⁴	x			x			x			x			x
Blood glucose and blood pressure measurement (group 2) (intensive diabetic control)	x	x	x	x	x	x	x	x	x	x	x	x	x
Funduscopy	x			x	x	x	x	x	x	x	x	x	x
BCVA (ETDRS)	x	x	x	x	x	x	x	x	x	x	x	x	x
Slitlamp	x	x	x	x	x	x	x	x	x	x	x	x	x
Fluorescein angiography	x						x						x
Fundus photography	x			x			x			x			x
OCT	x	x	x	x	x	x	x	x	x	x	x	x	x
Concomitant medication	x	x	x	x	x	x	x	x	x	x	x	x	x
AE/SAE (documentation & report)		x	x	x	x	x	x	x	x	x	x	x	x
SCR = Screening, to be performed within one week before study treatment start ¹ written informed consent has to be obtained before any study related investigations are performed ² for women of child-bearing potential a test will be performed at screening; all other women will be asked for pregnancy status. In the course of the trial women of child-bearing potential will be asked for pregnancy status before Ranibizumab treatment or fluorescein angiography ³ triglycerides, HbA1c ⁴ group 1 patients will be cared for diabetes by their general practitioner and will visit the site additionally every three months as indicated ⁵ checkup visit according to local practice & possible PRN therapy													

Table 3: Investigations during the clinical trial (months 12-24: follow-up time)

Visits/Months	13	14	15	16	17	18	19	20	21	22	23	24
Procedure	a time frame of ± 4 weeks is allowed until visit 24											
Ranibizumab treatment ¹	according to local practice & possible PRN therapy											
Clinical lab tests			X			X			X			X
Blood glucose and blood pressure measurement (group 1) (regular diabetic control)			X			X			X			X
Blood glucose and blood pressure measurement (group 2) (intensive diabetic control)			X			X			X			X
Funduscopy			X			X			X			X
BCVA (ETDRS)	X	X	X	X	X	X	X	X	X	X	X	X
Slitlamp	X	X	X	X	X	X	X	X	X	X	X	X

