Fluorescein angiography ¹						X						X
Fundus photography			X			X			X			X
OCT	X	X	X	X	X	X	X	X	X	X	X	X
Concomitant medication	X	X	X	X	X	X	X	X	X	X	X	X
AE/SAE documentation/reporting ²	X	X	X	X	X	X	X	X	X	X	X	X
¹ women of child-bearing potential will be asked for pregnancy status before each ranibizumab treatment or fluorescein angiography ² until 30 days after the patient has stopped the ranibizumab treatment												

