7.2.1. Documentation of adverse events and adverse drug reactions

All AEs occurring during the defined reporting period will be documented in the trial database/CRF including all information listed below.

The AE is documented including the following information:

- Date and time of onset and resolution
- Severity
- Causal relationship with IMP / study treatment
- Seriousness
- Interruption or withdrawal of study treatment and other measures taken

Regardless of whether a causal relationship between the AE and the IMP is suspected, trial subjects who develop adverse events must be monitored until all symptoms have been subsided, pathological laboratory values have returned to pre-event levels, a plausible explanation is found for the AE, the trial subject has died, or the study has been terminated for the trial subject concerned.

Preexisting diseases (before administration of the IMP) are not documented as adverse events but as concomitant diseases. New diseases and preexisting diseases that worsen during the trial are documented as AEs.

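### The AE recording window follows ranibizumab, which both arms receive, so it can close before month 24 while the randomised diabetes control and follow-up continue

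*Combined protocol and SAP*

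**What the plan says.** Section 7.1.1 defines the AE period: "All events occurring after the first administration of the IMP until 30 days after the patient has stopped the treatment must be documented". Footnote 2 to Table 3 (section 4.7.4.1) identifies the treatment meant. It runs "until 30 days after the patient has stopped the ranibizumab treatment" and is attached to the combined AE/SAE row for months 13 to 24. Section 7.2.1 links database entry to that period: "All AEs occurring during the defined reporting period will be documented in the trial database/CRF".

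Ranibizumab is not the randomised factor. Section 4.6.1 says: "In all patients (in both study arms) the diabetic macular edema will be treated with intravitreally given ranibizumab". The arms differ in diabetes control, which section 4.2 has Group 2 receiving at the trial site monthly in year 1 and every three months in year 2. Severe hypoglycaemia is one of the systemic AEs listed as a secondary endpoint in section 4.7.1.2.

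Other parts of the protocol set different limits:
- Section 7.2 has patients asked about AEs at every visit, then requires AEs to be entered in the medical records and the database or CRF, with no end date.
- Table 2 schedules AE/SAE documentation at visits 1 to 12 with no footnote about stopping.
- Section 7.1.3 runs SAE reporting from consent to 4 weeks after study participation ends, and section 7.3.1 requires every SAE during the trial to be documented.

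**The concern.** An AE window should cover the time during which the tested intervention can cause harm. Here that intervention is the diabetes control programme, and severe hypoglycaemia is its foreseeable harm. The window instead follows the drug common to both arms. If a patient's ranibizumab ends for good before month 24, the window can close while the programme and the monthly visits continue. An episode of severe hypoglycaemia not classed as an SAE could then be mentioned at a visit and, under sections 7.1.1 and 7.2.1, not be entered.

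At stake is the completeness of a named secondary endpoint in the second year. The planned analysis of it is modest: section 6.1.5 provides listings and contingency tables, and the synopsis adds a chi-square or Fisher test where applicable.

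**Working it through.** The plan gives no figure of its own on this point, so there is nothing to reproduce. The check asks which patients, which events and which visits are exposed.

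**Patients.** Definitive stops with continued follow-up are foreseen. Section 4.4 lists reasons for early discontinuation, among them no response after three monthly injections, and its note asks that patients still be followed up. Section 7.1.1 requires study medication to be stopped in pregnancy. A PRN pause is different. Section 4.6.1 discontinues injection when "no BCVA improvement in spite of treatment is seen after the first three injections", but keeps BCVA checks monthly and continues "Monthly injections are resumed when", followed by a condition. Table 3 describes ranibizumab in months 13 to 24 as "according to local practice & possible PRN therapy". The protocol does not define *stopped* against such a pause. If PRN eligibility to month 24 counts as treatment, the window stays open for these patients and nothing is lost.

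**Events.** SAEs are retained under 7.1.3 and 7.3.1, so only AEs that are not SAEs are exposed. Such episodes of severe hypoglycaemia can exist. Severity is graded in 7.2.2, separately from seriousness in 7.1.3, and the hospitalisation criterion in 7.1.3 excepts emergency outpatient treatment that meets no other SAE definition and leads to no admission.

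**Visits.** Table 2 schedules AE documentation at 12 visits (1 to 12) and Table 3 at 12 (months 13 to 24): 12 + 12 = 24. With a definitive stop at month *m*, the window closes about one month later.
- Going by the tables, Table 2 visits stay covered, so visits outside = min(12, 24 − (m + 1)).
- If 7.1.1 and 7.2.1 override both Table 2 and 7.2, visits outside = 24 − (m + 1).

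| Stop at month | Outside, by the tables | Outside, if 7.1.1 and 7.2.1 override |
|---|---|---|
| 3 | 12 of 24 (50%) | 20 of 24 (83%) |
| 6 | 12 of 24 (50%) | 17 of 24 (71%) |
| 12 | 11 of 24 (46%) | 11 of 24 (46%) |
| 18 | 5 of 24 (21%) | 5 of 24 (21%) |
| 23 or later | 0 | 0 |

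The counts are approximate, since Table 3 allows ±4 weeks per visit. If AE documentation ran to month 24 whatever the ranibizumab status, the count would be 0 for every stop month.

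**The case against.** The strongest objection is that the protocol already requires the recording. Section 7.2 requires documentation as well as enquiry, without a time limit. Tables 2 and 3 schedule documentation at all 24 visits, and 7.1.1 and 7.2.1 state what must be recorded without forbidding later entry. This stands in part. It confines the exposure by the tables to months 13 to 24. It does not remove it, because footnote 2 sits on the Table 3 row itself and closes it 30 days after ranibizumab stops. The two sets of text have to be reconciled.

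It can also be said that much severe hypoglycaemia would qualify as an SAE, since criterion 6 in 7.1.3 covers medically significant events. That is plausible, but the protocol neither defines severe hypoglycaemia nor classes it as an SAE, so it is left to case-by-case judgement.

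A reader might infer three stronger points, which the documents do not support:
- That the window closes at about month 13 for everyone, because the synopsis gives "12 months treatment period with Ranibizumab". The synopsis goes on to allow PRN treatment in follow-up, and Table 3 marks AE documentation at every month from 13 to 24. Nearly all of those marks would be void on that reading.
- That 71% to 83% of visits are lost after an early stop. This holds only if 7.1.1 and 7.2.1 override Table 2 and section 7.2.
- That the AE comparison is biased in a known direction, because section 2.1 hypothesises less re-treatment under intensified control. The documents give no stopping times by arm and no event rates, and the inference needs the last injection to count as the stop.

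**Conclusion.** The point holds for a limited group: patients who stop ranibizumab definitively before month 24 and remain in follow-up. For them, 7.1.1, 7.2.1 and footnote 2 do not require AEs that are not SAEs to be recorded after the 30 days, although the randomised diabetes control runs through year 2. Going by the tables, about 11 to 12 of 24 documentation visits fall outside the window after a stop at or before month 12, and fewer after a later stop. For patients who are only in a PRN pause, nothing is lost if that pause is not a stop.

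Separately, the text is inconsistent. Section 7.2 and Table 2 set no stop-related limit, while 7.1.1, 7.2.1 and footnote 2 do. Footnote 2 also applies to SAEs, whose window in 7.1.3 runs to 4 weeks after study participation ends.

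The number of patients affected, the share of severe hypoglycaemia not classed as an SAE, and the direction of any difference between arms cannot be derived from the documents. The primary endpoint is not affected. Severity is minor, and the change is a cheap improvement.

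**What to change.** Reconcile sections 7.1.1, 7.1.3, 7.2 and 7.2.1 with footnote 2 of Table 3:
- State in 7.1.1 and footnote 2 that AEs, or at least the named AE endpoints including severe hypoglycaemia whether or not serious, are documented in both arms to the month-24 visit, or to the last follow-up contact if that is earlier, whatever the ranibizumab status. Where 30 days after the last injection falls later, documentation runs to that date.
- Say explicitly that follow-up after a discontinuation under section 4.4 is included. That section discontinues patients from study participation yet asks that they be followed up, so a rule worded only as the end of participation would leave them unclear.
- Remove SAEs from footnote 2 so that it agrees with 7.1.3.
- Compare the named AE endpoints by arm over this common window.

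The cost is a change of wording in the safety section and one table footnote, plus slightly more AE entry for patients no longer on ranibizumab. AE documentation visits are already scheduled monthly to month 24, so no visits are added.
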